Retention, Tracking, and Attrition: Although participants can withdraw at any time, steps will be used to minimize dropouts to ensure high internal validity. Participant progression will be tracked. Staff will use behavioral reinforcement strategies known to be effective in the behavior change literature¹⁵⁸⁻¹⁶⁰ and be trained to develop rapport with participants by communicating expectations for participants and staff. Personalizing this relationship will enable participants to be more direct about problems, providing a strong foundation for problem-solving. While drop-out rates vary among youths with SCD,^{57,161} we conservatively planned for 20% attrition. Our method of tracking and multiple contacts will help us retain some of these participants for intent-to-treat purposes, despite their discontinued app use. Participants will provide contact information for one individual who can always contact them and update contact information at each assessment. If they do not respond to email/text reminders, we will follow-up by phone. Finally, we will create a dummy coded variable for each respondent where 1=completers and 2= drop outs and test for associations with key variables in our analytic models. If bias is identified, we will control for it by adding it as a covariate.

Compensation: All participants (n=100) will be compensated to incentivize and improve study retention. A \$20 gift card will be given to the teens after each study assessment (baseline, 6-week, and 12-week) for a total compensation of \$60. Parents will be provided a \$10 gift card after each study assessment for a total of \$30.

App Use: Implementation of technology-based interventions can be challenging due to participants forgetting, fatiguing, or believing they have learned all they need to know. In order to bolster compliance with using either of the assigned app, weekly reminders to use the app will be sent to participants by text message.

3C.7.4. Safety Considerations. Participant safety is a priority. This study will include a Data and Safety Monitoring Plan (DSMP). The team will monitor progress, discuss concerns, and take corrective actions. [name] (PI) is a licensed psychologist and will assemble a group of experts including at least one licensed mental health professional, physician, and biostatistician. Participants who express emotional or physical distress will be

FIGURE 7: Schedule of Measurements

Assessment	Screening	Pre-test/Baseline	Week 6	Week 12/Post-test

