Inclusion Screener*	X			
Communication and SCD Pain Knowledge measure**		X	X	X
Pain Assessment Tool		X	X	X
SCD Transition Program Questionnaire		X	X	X
SCD Transition Knowledge Questionnaire		X	X	X
Sickle Cell Self-efficacy Scale		X	X	X
Family Cohesion Scale		X	X	X
CDC Flu IQ Questionnaire		X	X	X
App Usage			X	X
System Usability Scale			X	X

* Completed by parent only

** Completed by teen and parent

referred to their treating physician immediately. Based on our experience and demonstrated ability to conduct this type of research, we are confident we can achieve safe intervention delivery.

3C.8. Data Collection, Management, and Security. KB has used online data collection successfully in a number of studies. Study consents and pretests and posttests will be collected online via participants' personal smartphone or tablet. Surveys will be programmed using QuestionPro software on KB's secure web server to ensure a structured approach and reduce errors/missing values. All procedures will be approved by KB's IRB.

KB has considerable experience maintaining large databases and ensuring high-quality data. [name], KB's Biostatistical Manager, will supervise data management. All data will be uploaded in real-time using KB's secured network; data will be de-identified and stored in KB's secured database. Established KB protocols for quality assurance (valid ranges; internal consistency checks, etc.) will ensure high quality data. The KB data team will compile master data files. Survey and app usage data will be linked. Missing data should be limited since data is recorded electronically. Staff will identify missing responses and check that entries were not intentionally skipped. Analyses will be done on data collected. While unlikely, data may not be missing at random (NMAR). KB will assign all lost responses to extreme category and perform multiple imputation procedures that can handle various amounts of missing data and use covariates and propensity scores.

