Sample size: The primary outcome is detecting a positive change on the knowledge acquisition questionnaire (communication skill and pain identification). To be conservative, we assumed that 80% of those offered the app will have baseline and post-test results. Our sample size of 100 allows for up to 20% dropouts. We expect results similar to those found by Barakat et.al.¹⁵⁹ on our secondary outcome measures (which were similar to ours). We used their results to derive our nonparametric sample sizes on SCD disease-specific and transition knowledge, and family cohesion. For the transition knowledge construct, assuming the correlation before-to-after is 0.5, the sample size is N=22, using power of 80% and a Bonferroni corrected Type I error of 0.0167. For disease-specific knowledge, the sample size necessary to achieve 80% power is 76 participants, using the same assumptions (Type I error of 0.0167). For the third outcome (i.e., family cohesion), if we assume 80 participants at all time points, then the power is somewhat lower since the sample size required to achieve 80% power is 132 (mean difference between post-test and baseline was 6.51 with a pooled standard deviation of 22.8). For this outcome, the power with 80 participants is 54%. We weighed the importance of the first two outcomes (disease-specific and transition knowledge) relative to the increase in cost and duration to increase the sample to 165 (i.e., 132 plus dropouts up to 20%) to account for the single-item family cohesion variable. We felt that having greater than 50% power for family cohesion and sufficient power for the participant-related measures (80% for SCD disease-specific and transition knowledge), we would not increase the sample size by 65% (i.e., from 100 to 165) in order to achieve 80% power for family cohesion. We have nevertheless left it in, because we respect its importance. As a Phase II study, we believe that we can accept less power on that single measure given consistency of outcomes will drive further evolution of this product.

Analyses: There are 2 aims that will be evaluated (AIMs 2 and 3). As a Phase II SBIR, the analyses are heavily descriptive in nature for this trial. Means (standard deviations), medians (interquartile range), distributions, frequencies and percentiles, etc. will be used to characterize the outcome measures.

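### Dropout adjustment depends on a weak completer-versus-dropout test, and the indicator it would add does not correct the change estimate

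*Combined protocol and SAP*

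**What the plan says.** The rule is in protocol section 3C.7.3, under Retention, Tracking, and Attrition, and has two steps. First: "we will create a dummy coded variable for each respondent where 1=completers and 2= drop outs and test for associations with key variables". Second: "If bias is identified, we will control for it by adding it as a covariate". Neither a significance level nor a criterion for bias is given, and the key variables are not listed.

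The same section says "we conservatively planned for 20% attrition". The SAP's sample-size paragraph agrees: "Our sample size of 100 allows for up to 20% dropouts".

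Section 3C.8 adds separate text on missing data. It states "Analyses will be done on data collected", then allows that data may not be missing at random (NMAR), and continues: "KB will assign all lost responses to extreme category and perform multiple imputation procedures that can handle various amounts of missing data". It does not mention the dropout test.

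The SAP names neither imputation nor a dropout covariate. It plans to test within-person change, to use linear regression for age, sex and education, and to examine the characteristics of dropouts for what they reveal about the app.

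**The concern.** This is a test-then-adjust rule, and it can fail at either step. A non-significant test on 20 dropouts is weak evidence of similarity, yet the plan would take it as a reason not to adjust. A significant test brings in a term that, in the likely analyses, cannot move the estimate towards the value for all enrolled teens.

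The trial has one arm, so its main result is a mean change. No control group exists in which similar attrition might offset a shift, and selective dropout passes straight into the estimate.

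**Working it through.** **Inputs from the documents.** 100 enrolled and 20% attrition (section 3C.7.3; SAP, Sample size), giving 100 × 0.20 = 20 dropouts and 80 completers. Pre-post correlation 0.5 (SAP).

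**Assumptions.** A two-sided test, with level 0.05 and a range shown; a completer-dropout difference of 0.5 SD, with a range shown. The documents give neither.

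**The plan's own figures.** No power is stated for the dropout test. The sizing that can be checked is family cohesion. SD of change = 22.8 × √(2 × (1 − 0.5)) = 22.8, and 6.51/22.8 = 0.286. A two-sided paired t-test at 0.0167 gives N = 132 and 54.5% power with 80 teens (stated: 132 and 54%). Dropout inflation gives 132/0.80 = 165 and 80/0.80 = 100, as stated. These all reproduce.

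**Step 1: what the test can see.** The standard error of the standardised difference is √(1/20 + 1/80) = 0.25. For 0.5 SD the noncentrality is 0.5/0.25 = 2.0. Power is 51.6% by the normal approximation and 50.8% by the t distribution on 98 df. Power by t:

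| True difference | level 0.0167 | level 0.05 | level 0.10 |
|---|---|---|---|
| 0.3 SD | 11% | 22% | 33% |
| 0.5 SD | 34% | 51% | 63% |
| 0.7 SD | 64% | 79% | 87% |

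The difference detectable with 80% power at 0.05 is (1.96 + 0.84) × 0.25 = 0.70 SD. The approximate 95% interval half-width is 1.96 × 0.25 = 0.49 SD, so even an observed difference of zero is compatible with almost half an SD either way. With other numbers of dropouts out of 100 (0.5 SD, level 0.05), power is 32% for 10, 42% for 15, 57% for 25 and 62% for 30.

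**Step 2: what the indicator does if the test is positive.**
- *Baseline-to-12-week change among teens with both scores.* Every such teen is a completer. The indicator is constant and collinear with the intercept (the two columns have rank 1), so the estimate cannot change.
- *Repeated-measures model that keeps dropouts' baselines.* The indicator's main effect gives dropouts their own level. A dropout with only a baseline score then carries no information about change, and the estimate returns to the completers' own change.

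**Step 3: size, by illustration.** Dropouts start 0.5 SD lower, correlation is 0.5 with equal SDs (slope of change on baseline −0.5), and true mean change in all enrolled is 0.30 SD.
- The all-enrolled baseline mean lies 0.20 × 0.5 = 0.10 SD below the completers' mean. Completers' expected change is 0.30 − 0.5 × 0.10 = 0.25 SD.
- The SD of change is 1, so the standard error with 80 teens is 1/√80 = 0.112. The bias is 0.05/0.112, about 0.45 of a standard error.
- Simulation (20,000 trials): completers only 0.249 (SD 0.112); baseline-adjusted to the all-enrolled mean 0.299 (SD 0.110).
- Random-intercept model (1,000 trials): 0.298 without the indicator, 0.249 with its main effect.

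**Step 4: the part due to the gate.** Suppose a positive test led to a valid baseline adjustment, which is kinder than the stated rule. The gated estimate then averages 0.284 and the test fires in about 50% of trials. The gate costs 0.299 − 0.284 = 0.015 SD, or 0.015/0.112 = 0.13 of a standard error.

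**The case against.** A reader might infer that attrition bias is corrected only when the test is positive, and so is left uncorrected in about half of trials. The documents do not support that. Section 3C.8 plans imputation with covariates and propensity scores without reference to this test, section 3C5.1 includes demographics as covariates unconditionally, and section 3C.7.3 aims to keep some teens who stop using the app in follow-up. Nor would a positive test bring a correction: in a complete-case analysis the indicator does nothing, and in a repeated-measures model a negative result would leave the better estimate in place.

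The reply on section 3C.8 is partial. Its imputation text sits beside the statement that analyses use the data collected, is introduced in connection with NMAR data, and combines extreme-category assignment with multiple imputation, which are different treatments of the same lost responses. The SAP repeats none of it. That is too unclear to count as the primary handling of dropout, but it rules out saying that no other handling exists.

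A reader might also fault the gate for false alarms: ten independent key variables tested at 0.05 give 1 − 0.95^10 = 40%. The count and the independence are assumptions, and an unneeded baseline adjustment costs no precision in the illustration. Nor did ignoring the pretest visibly harm interval coverage: an approximate 95% interval around the gated estimate still covered 0.30 in 95% of simulated trials.

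Finally, the SAP calls the analyses largely descriptive, and the bias in this example understates the app's benefit. Both points limit the severity. The direction, however, follows from assuming that dropouts start lower; if they started higher, it would reverse.

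**Conclusion.** The point holds in a limited form. The rule in section 3C.7.3 does not reliably protect a single-arm change estimate: the test has about 51% power for 0.5 SD at the planned attrition, and the indicator it would add is inert or counterproductive in the analyses the plan could be running. The SAP does not fill the gap.

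The size is modest: about 0.05 SD, or half a standard error, when dropouts differ by 0.5 SD at baseline. It would be 0.20 × 0.5 = 0.10 SD if dropouts' change itself differed by 0.5 SD. The weak gate explains little of this (about 0.015 SD); the larger part comes from resting the result on completers. The figures depend on the assumed 0.5-SD difference, the two-sided 0.05 level and the SAP's correlation of 0.5.

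**What to change.** Replace both sentences in section 3C.7.3, the test and the conditional adjustment. Deleting only the condition would leave an unconditional dropout indicator, which Step 2 shows to be useless or harmful.

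1. Regardless of any test, name one primary change analysis in the SAP, without the dropout indicator. Either fit a change model with baseline score, age, sex and education, estimated at the covariate means of all enrolled teens; or, to the same end, fit a likelihood-based repeated-measures model using all baseline, 6-week and 12-week data.
2. Make the imputation in section 3C.8 a sensitivity analysis, and reconcile that section's wording with the SAP.
3. Report completer-dropout differences descriptively, as standardised differences with 95% confidence intervals, and do not let their p-values decide the model.

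The cost is a few sentences and a few more model terms. No extra teens or data are needed, and the illustration shows no material loss of precision (SD 0.110 against 0.112). The limit is that this corrects only dropout related to measured variables. NMAR dropout remains a matter for the sensitivity analysis.

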6-week interim assessment: Participants will complete interim assessments of initial changes (i.e., teens to complete all measures; parent to complete the single proxy measure assessing their child's knowledge acquisition). An invitation email and text messages containing a link to the surveys along with their unique password (PIN number) will be sent. Participants will complete the web-based surveys using either their tablet or smartphone; no video meeting will be required. Participants who do not complete the surveys within 3 days will receive an email and text reminder (and 3 more reminders at 3-day intervals if still not completed).

12-week post-test assessment: Participants will complete a post-test assessment via videoconference. They will meet individually with a study staff to complete the online surveys and a brief post-test interview.

3C.7.2. Outcomes: Baseline, Interim, and Post-test Measures. The baseline, 6-week interim, and 12-week post-test surveys will use a measure created by the investigative team and EAB as the primary outcome (i.e., knowledge acquisition for communicating about pain and types of pain). Secondary outcomes will be the app Pain Assessment Tool (PAT) and validated measures of SCD knowledge, disease self-efficacy, and family cohesion. Surveys should take 30 minutes to complete (see **Figure 7** and **Appendix E**).

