services. It is designed to assess SCD knowledge in seven areas: (1) pathophysiology, (2) genetics, (3) physical symptoms, (4) treatment, (5) self-care, (6) psychosocial and developmental issues, and (7) health care delivery. It has good psychometric properties.^{153,154} Higher scores represent greater knowledge.

Sickle Cell Self-efficacy Scale: This instrument, used to assess self-efficacy in adolescents with SCD,¹⁵⁵ is comprised of nine questions measuring participants' perceptions of their ability to function on a day-to-day basis and to manage SCD symptoms (e.g., pain). The instrument is reliable and valid for assessing adolescents' self-efficacy for engaging successfully in day-to-day activities despite having SCD.

Family Cohesion: Family cohesion will be assessed by the single item Family Cohesion scale from the Child Health Questionnaire (CHQ)¹⁵⁶, a pediatric quality of life (QOL) survey that has been normed for children age 5 to 18 years including those with chronic diseases. The CHQ consists of 28 items that assess 14 different concepts regarding child and family physical and psychosocial well-being. There is evidence of good reliability and validity of this measure¹⁵⁶ including the single-item Family Cohesion question.¹⁵⁷ This scale, which rates a family's ability to get along with one another, uses a single item ("In general, how would you rate your family's ability to get along with one another?") rated on a 5-point scale. The PAT is assessing QOL, therefore to reduce duplication of information and study burden only the Family Cohesion item will be administered.

CDC Flu IQ measure: This is a 10-item quiz developed by the Centers for Disease Control to assess general knowledge about influenza and vaccination. It will serve as a nonequivalent dependent variable.

App Usage: App use will be monitored using Web Trends software; tracking macro and micro level data. It will record how users move through the program including the time spent on each activity, response latency to individual items, and scores achieved on games. Summaries of these data (means, ranges) will be reviewed to understand usage patterns. Teens will be sent "push notifications" to encourage app use. Users will evaluate the app on the **System Usability Scale** at the 6- and 12-week assessment.¹⁴²

3C.7.3. Adherence, Dropouts, and Participant Compensation.

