Any survey questions and discussion transcripts will be de-identified before being submitted for analysis and the Research Assistant will remove any references to individual names or identifier data. There are no clinical data to be captured. Responses to survey questions and participation in discussions will not reasonably place the subjects at risk of criminal or civil liability or be damaging to the subjects' financial standing, employability, or reputation. The data collected on this project will be obtained with the "use of educational tests, survey questions and interview procedures."

To protect privacy and to ensure that the participant is the person completing the app activities, KB will uniquely identify the user's smartphone/tablet based off the device's "hardware footprint". The app will upload all app activity data to the KB secured web server database.

All surveys and data collection forms will be IRB-approved and administered under the supervision of senior project staff. Participants will be told that they do not have to answer any questions which make them uncomfortable and can terminate their participation at any time they wish. Notes, surveys, and data will be accessible only by research personnel. All notes will be stored in locked cabinets; all electronic data files will be stored on KB's secure network servers behind computer firewalls, with routine backup. All identifiers will be stored in secure files and behind computer firewalls and results will be shared in aggregate form only.

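### Three treatments of missing data are named without saying which is primary, at what level or which extreme, and the dropout covariate would not control attrition bias

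*Combined protocol and SAP*

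**What the plan says.** Section 3C.8 treats missing data in a few adjacent sentences. It expects little of it, because entry is electronic, and has staff check for skipped entries. It then says: "Analyses will be done on data collected. While unlikely, data may not be missing at random (NMAR"). Next comes the rule: "KB will assign all lost responses to extreme category and perform multiple imputation procedures", with covariates and propensity scores.

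Section 3C.7.3 deals with attrition. It plans for 20% and hopes to "retain some of these participants for intent-to-treat purposes, despite their discontinued app use". It creates a dummy coded 1 for completers and 2 for dropouts and tests it against key variables. Its remedy is: "If bias is identified, we will control for it by adding it as a covariate".

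The SAP contains no missing-data method. Its sample-size paragraph assumes that 80% will have baseline and post-test results, and for family cohesion it works out power with the words "if we assume 80 participants at all time points". Its analysis paragraphs test within-person change, compare the characteristics of dropouts descriptively, and repeat the primary analysis on the CDC Flu IQ.

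**The concern.** A value set to an extreme is no longer missing, so it cannot also be imputed in the same analysis. The two steps can coexist as separate analyses, or at different levels (skipped items and missed visits), but the plan does not say that this is meant. It also leaves open whether the extreme is the lowest or the highest category.

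There is no control arm, so the mean within-person change is the result, and no second group shares whatever distortion the missing-data rule brings. Lowest assignment at week 12 could turn a gain into a loss, and highest assignment could create or inflate one. The Flu IQ, which is expected not to change, would be moved by the same rule and become harder to read as a check.

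The covariate sentence is a separate matter. It would let a report state that attrition bias had been controlled when it had not.

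**Working it through.** **1. The SAP's own figure.** Inputs from the SAP sample-size paragraph: family-cohesion difference 6.51, pooled SD 22.8, Type I error 0.0167, power 80%. The correlation of 0.5 is stated there for transition knowledge and assumed here for family cohesion.
- SD of change = 22.8 × √(2 × (1 − 0.5)) = 22.8.
- A two-sided paired t test (noncentral t) needs N = 132 for 80% power and has 54.5% power at n = 80. The SAP gives 132 and 54%.
- 132/0.8 = 165 and 80/0.8 = 100, also as stated.

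The sizing reproduces, so nothing here rests on a sample-size error.

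**2. Extreme assignment of missed week-12 scores.** An SD of 22.8 cannot come from a raw 5-point item, so a 0-100 scale is assumed. Let m be the baseline mean (assumed 50-70) and f the share lost at random, with a true gain of 6.51.
- Lowest: mean change = (1 − f)(m + 6.51) − m.
- Highest: mean change = (1 − f)(m + 6.51) + 100f − m.
- Lowest assignment gives zero change at f = 6.51/(m + 6.51).

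| m | Lowest, f = 0.20 | Highest, f = 0.20 | Loss that erases the gain |
|---|---|---|---|
| 50 | -4.8 | +15.2 | 11.5% |
| 60 | -6.8 | +13.2 | 9.8% |
| 70 | -8.8 | +11.2 | 8.5% |

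The observed data would give +6.51 in every row. The planned attrition of 20% exceeds every figure in the last column.

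**3. Flu IQ under the same rule.** It has 10 items. Assume a mean of 5-7 correct, no true change and 20% lost. Lowest gives −0.2 × (5 to 7) = -1.0 to -1.4. Highest gives 0.2 × (5 to 3) = +1.0 to +0.6.

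**4. Skipped items only.** With skip rates s0 at baseline and s12 at week 12, a 0-100 score and no true change, the shift is −(s12 − s0)m for lowest and (s12 − s0)(100 − m) for highest.
- Equal rates cancel.
- A rise from 1% to 5% gives −0.04 × (50 to 70) = -2.0 to -2.8, or 0.04 × (50 to 30) = +2.0 to +1.2.
- The exception is family cohesion: "Family cohesion will be assessed by the single item Family Cohesion scale", so a skipped item is the whole score and the formulas in step 2 apply.

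**5. The dropout dummy in a change analysis.** Among teens with both scores who are all coded completers, the dummy takes one value. It cannot be separated from the intercept. Suppose completers gain 6.51 and the 20% who drop out gain 0. The mean for all enrolled is 0.8 × 6.51 = 5.21, the estimate is 6.51, and the bias is 1.30 with or without the dummy.

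**6. The dummy as a main effect in a repeated-measures model.** The plan names no such model. Assumptions: compound symmetry with r = 0.5; completers gain 0.20 SD at week 6 and 0.40 SD at week 12; 20% dropouts with no gain. The target is 0.8 × 0.40 = 0.32 SD. Exact generalised least squares gives these estimates (SD units), without and with the dummy:

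| Dropouts seen at | Equal baselines | 0.3 SD lower | 0.5 SD lower |
|---|---|---|---|
| Baseline only | 0.400 / 0.400 | 0.430 / 0.400 | 0.450 / 0.400 |
| Baseline and week 6 | 0.387 / 0.380 | 0.407 / 0.380 | 0.420 / 0.380 |
| Same, and half at week 12 | 0.350 / 0.345 | 0.359 / 0.345 | 0.364 / 0.345 |

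The share of bias removed is (without − with)/(without − 0.32). It is 0-16% with equal baselines and 27-44% when dropouts start 0.3-0.5 SD lower. The dummy absorbs the difference in level, not the difference in change.

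**The case against.** The strongest reply is that 3C.8, read in order, already has a default: analyse what was collected, and turn to extremes and imputation only if data seem not to be missing at random, which the plan thinks unlikely. The SAP's power for 80 participants fits that. The paragraph is about data management and survey entries, while attrition has its own section. If every missed visit received an extreme value in the main analysis, the other two treatments would be redundant.

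Most of this stands. A reader might infer that the plan will set missed week-12 visits to an extreme in its primary analysis, or that it has no default at all. The documents do not support either inference. They show a default that is not labelled. What remains is that the rule speaks of all lost responses without limiting it to items, that the contingency has no trigger, and that observed data cannot establish missingness not at random. The choice could therefore be made after results are seen. If the rule covers items only, the plan has no stated method for the attrition it expects.

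It is also fair to say that item-level harm needs skip rates to change between visits. Section 5B.2 allows refusals ("Participants will be told that they do not have to answer any questions which make them uncomfortable"), but a refusal is not clearly a lost response. At week 6 "no video meeting will be required", yet baseline and week 12 are both staffed video sessions. Nothing in the documents shows that skipping would rise between them.

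Finally, the primary measure is not yet built, and the SAP calls the analyses largely descriptive. That limits how much weight the point-scale figures can bear.

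**Conclusion.** The concern holds as a gap in specification, worth closing before outcomes are seen. The primary method, the level and the extreme are unlabelled, and the SAP does not supply them.

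The large distortions in steps 2 and 3 are conditional on the visit-level reading. They also rest on an assumed 0-100 family-cohesion scale with baseline mean 50-70, an assumed Flu IQ mean of 5-7, and loss at random. On the item-level reading the harm is small unless skip rates differ, apart from the single-item family-cohesion score.

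The claim that the dummy controls attrition bias is not supported. A reader might infer that the covariate at least removes part of the bias. For the baseline-to-week-12 change in teens with both scores, all coded completers, it removes none. Partial removal needs a repeated-measures model, and most of the bias stays under the assumptions of step 6. Dropout is also undefined: if teens who stop the app but are still assessed are coded 2, the dummy varies at week 12, and as a main effect it still leaves most of the bias.

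**What to change.** In the SAP:
- Name one primary method that uses all observed baseline, 6-week and 12-week scores, including those of teens who stop the app but are still assessed. A mixed model would serve, or the multiple imputation that 3C.8 already mentions.
- Remove extreme assignment from the primary analysis. If it is kept, report it only as a labelled pair of sensitivity bounds, all lowest and all highest.
- If it was meant only for skipped items, say so, name the extreme for each scale, and exclude the single-item family-cohesion score.
- Apply the same rule to the Flu IQ.
- Define dropout: left the study, or stopped the app.

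In 3C.7.3, delete the statement that the dummy controls bias. Rely on the descriptive dropout comparison already in the SAP and on the sensitivity bounds. Delta-adjusted imputation, or a dummy-by-time term averaged over both groups, is optional.

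The cost is protocol and SAP wording and slightly more analysis work. Data collection does not change.
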